6.6 Blood Draw for Morning Trough Concentrations

Blood samples will be collected for morning trough concentrations (C_{12}) of cortexolone 17 α -propionate and cortexolone in plasma at Screening, Day 1 (pre-dose), Day 7 and Day 14.

6.7 Physical Examination, Vital Signs, ECGs and Safety Laboratory Tests

Findings from the physical examinations will be recorded in medical history (from assessment at Screening) or as AEs (from assessment at Day 14 (EOS)).

Vital Signs, ECGs, and safety laboratory data are to be collected at Screening and Day 14 (or EOS). Urine pregnancy test (UPT) for women of childbearing potential (WOCBP) will be performed at Screening, Days 1 and 14.

6.8 Concomitant Medications and Concurrent Therapies/Procedures

Details of prior and concomitant medication use and concurrent therapies/procedures will be collected throughout the study.

7 STATISTICAL METHODS

7.1 General Considerations

This section presents the statistical approaches that are anticipated for the analysis of the study data. These approaches may at times require modifications due to unanticipated features of the data. Deviations from analyses summarized in this document will be noted in the CSR.

Version 9.4 (or higher) of the SAS statistical software package will be used to provide summary tables and data listings, unless otherwise stated.

For continuous variables, descriptive statistics will include the number of subjects with non-missing data (n), mean, median, standard deviation, minimum and maximum values. For categorical variables, the number and percentage of subjects within each category will be presented. Subject data listings sorted by study site and subject number will be presented. Summaries and analyses will be provided as specified below.

7.2 Analysis Populations

All subjects will be classified into the Safety, Evaluable, and Pharmacokinetic (PK) populations according to the following definitions.

7.2.1 Safety Population

The Safety population will include all enrolled subjects who were dispensed and applied at least one dose of the test article.

7.2.2 Evaluable Population

The evaluable population will include those subjects in the safety population who have both Screening and Day 14 serum cortisol data (pre- and post-cosyntropin stimulation) and meet the following criteria:-

- Meets all inclusion/exclusion criteria, including normal response to cosyntropin stimulation defined as a Screening CST with a 30-minute post-stimulation cortisol level of > 18 µg/dL.
- Screening and Day 14 CST were conducted between 7-9 AM.
- Day 14 CST was conducted within ±1 hour of the Screening CST.
- Applied at least 80% of expected applications and applied the final dose no more than 14 hours prior to the start of the CST test.
- Has not taken or applied any medications that may interfere with HPA axis function.
- Do not have any other significant protocol deviations.

HPA axis suppression analysis will be conducted on the Evaluable population.

7.2.3 Pharmacokinetic Population

The PK population will include those subjects in the Safety population who have at least an 80% dose compliance based on number of applications, have at least one post-baseline PK blood draw within ±2 days of the scheduled visit at Days 7 and 14, and do not have any significant protocol deviations. For subjects who are in the PK population but did not apply the final three doses prior to the PK blood draw at Day 14, their Day 14 data will be excluded. For subjects in the PK population who discontinued from the study prematurely, their Screening, Day 1 and Day 7 data will be included as long as their dose compliance up to Day 7 is at least 80%.

The morning trough concentrations of cortexolone 17α-propionate and cortexolone will be presented for the PK population.

7.3 Final Analyses and Reporting

Final database lock will occur after all subjects have completed the study assessment period (or discontinued early) and all subject data has been monitored. Analysis may not occur until after database lock, this SAP is approved, and analysis populations have been identified.

7.4 Methods for Handling Missing Data

All summaries and analyses will use observed data only.

7.5 Sample Size

No formal sample size calculations were performed. The number of evaluable subjects (20) is historically consistent with other HPA/PK studies.

7.6 Subject Disposition

The number and percentage of subjects who were enrolled in the study, who completed the study, who withdrew from the study and their reasons for discontinuation will be tabulated for each analysis population.

Subject data listings of the protocol deviations, if any, and analysis population identification will be provided.

7.7 Screening and Baseline Assessments

7.7.1 *Demographics*

Demographic information including age, sex, ethnicity, race will be summarized for each analysis population. The demographic data for screen failures will be listed separately.

7.7.2 *Medical History, Dermatological Examination and Physical Examination*

Medical history, dermatological examination, and abnormalities noted during the physical examination at Screening will be presented in subject data listings for the Safety population.

7.7.3 *Baseline Vital Signs, Height and Weight*

Descriptive statistics will be provided for Baseline vital signs (blood pressure, pulse rate, temperature, and respiration rate), height, weight and BMI for the Safety population.

7.7.4 *Baseline Clinical Evaluations*

Baseline IGA and inflammatory and non-inflammatory lesion counts will be summarized for the Safety population.

Baseline LSRs will be tabulated for the Safety population.

7.7.5 *Extent of Exposure*

The total amount of test article used by each subject (difference between the weight of the tubes dispensed and weight of the tubes returned) and the mean daily amount of test article applied (total amount of test article used divided by the treatment duration) will be calculated. The treatment duration is calculated by last dose date - first dose date +1. Descriptive statistics will be used to summarize the total amount and mean daily amount of test article applied for each analysis population.

7.7.6 *Dosing Compliance*

Dosing compliance (%) is derived by the following formula:

$$\frac{\text{Total number of applications}}{\text{expected applications}} \times 100,$$

where expected applications are 26 considering 13-day course of planned treatment for subjects who completed the study; and (study day of the last dose)x2 for subjects who discontinued from the study prematurely.

Descriptive statistics will be used to summarize test article dosing compliance. Subjects who applied at least 80% of the expected applications will be considered to be compliant with test article dosing.

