#### **18.3.3.2 Dosing Compliance**

Descriptive statistics will be used to summarize test article compliance for the Safety, PK, and evaluable populations. Measures of test article compliance will include the duration of treatment, the total number of applications (determined from the actual number of applications reported by the subject), and the percent of expected doses applied. A subject will be considered compliant with the dosing regimen if the subject applies at least 80% of the expected number of applications prior to the HPA assessment. Subjects included in the PK analysis (PK population) must not have any significant protocol deviations, must have at least an 80% dose compliance based on number of applications, and must apply the final three doses as prescribed prior to the end of study PK assessment.

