5 DEFINITIONS

- End of Study (EOS): Visit 4 or Early Termination Visit
- Completed Subject: A subject is considered to have completed the study if the subject completed the study treatment.
- Study Day: The study day is the day of study relative to the first dose (Baseline visit/Day 1) of the test article.
Study Day = follow-up visit date – first dose date + 1
- Baseline in Change from Baseline: The baseline assessment in change from baseline is defined as the last non-missing measurement collected at Screening or Day 1 visit prior to the test article application.
- Treatment Area: The area defined by the investigator to which the test article is applied and which includes the face and trunk.

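### For children who discontinue, SAP 7.7.6 leaves out doses due after the last-dose day, so the 80% check can admit a Day 7 trough drawn long after dosing stopped

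*SAP*

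**What the plan says.** SAP 7.7.6 defines compliance as applications made divided by expected applications. For completers: "where expected applications are 26 considering 13-day course of planned treatment for subjects who completed the study". For the rest, the denominator is "study day of the last dose)x2 for subjects who discontinued from the study prematurely". SAP Section 5 counts study days from the first dose (Day 1), and it ties completion to treatment: "A subject is considered to have completed the study if the subject completed the study treatment". The threshold is 80%.

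SAP 7.2.3 uses this percentage to decide which concentrations are analysed. A premature discontinuer's Screening, Day 1 and Day 7 values stay in "as long as their dose compliance up to Day 7 is at least 80"%. No separate formula is given for that check. The same section drops Day 14 data when the last three doses before the Day 14 draw were not applied, but has no matching rule for Day 7. It also excludes children with significant protocol deviations, without defining them. SAP Table 1 places the Day 7 draw 12 h ± 30 min after the previous evening's dose.

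Protocol 18.3.3.2 anchors compliance to the assessment instead: "at least 80% of the expected number of applications prior to the HPA assessment".

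**The concern.** The discontinuer's denominator is fixed by the child's own last dose, not by what was due before the sample. A run of missed doses immediately before the draw is the pattern that most distorts a trough, and it is the pattern this formula cannot see.

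The protocol makes the situation possible. Section 6.3 and Appendix 3 (A 3.5) tell subjects to stop use if irritation or rash develops, and Section 14.2 lists noncompliance as a reason for withdrawal. Section 10.3 lists the Visit 3 blood draw before tube weighing and before the supervised application. A child who stopped days earlier can therefore be sampled and then withdrawn without a further dose. Trough concentration is a primary safety endpoint (Protocol 18.2.2), and the error would understate exposure.

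**Working it through.** **Plan's own figure.** 13 days × 2 = 26 expected applications for completers, which matches SAP 7.7.6. The 80% threshold needs 0.8 × 26 = 20.8, so 21 applications.

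**Inputs.** Dosing is every 12 hours from Day 1 (SAP Section 4). Taking two applications on Day 1, as the figure of 26 implies, 6 × 2 = 12 are due before a Day 7 morning draw. Passing 80% of 12 needs 10.

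**Formulas.** SAP: 100 × applied / (2 × study day of last dose). Comparison: 100 × applied / 12. Time since last dose at the draw: 12 h × (13 − position of the last dose), where Day 1 AM is position 1 and the Day 7 morning draw falls at position 13.

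| All doses applied to, then none | Hours since last dose | SAP 7.7.6 | Of 12 due |
|---|---|---|---|
| Day 3 PM | 84 | 6/6 = 100% | 6/12 = 50% |
| Day 4 PM | 60 | 8/8 = 100% | 8/12 = 66.7% |
| Day 5 AM | 48 | 9/10 = 90% | 9/12 = 75% |
| Day 5 PM | 36 | 10/10 = 100% | 10/12 = 83.3% |
| Day 6 AM | 24 | 11/12 = 91.7% | 11/12 = 91.7% |

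The first three rows pass under the SAP formula and fail against doses due. The last two pass either way, although both samples are well outside 12 h ± 30 min. Correcting the denominator alone is therefore not enough.

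**Missed doses that are counted.** Three missed of 12 with the last dose on Day 6 PM gives 9/12 = 75%. Mornings only on Days 1 to 6 gives 6/12 = 50%. The first dose alone gives 1/2 = 50%. All three fail.

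**All patterns.** With the first dose always applied, the other 11 doses give 2^11 = 2,048 patterns. Of these, 127 pass the SAP formula and 67 pass with denominator 12. All 60 that differ have the last dose on Day 5 or earlier. These are counts of patterns, not probabilities.

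**Random missing (assumed rates).** If each later dose is missed independently with probability 10%, 20% or 30%, the chance of passing is 0.916, 0.642 or 0.353 under the SAP and 0.910, 0.617 or 0.313 with denominator 12. For scattered misses the two rules nearly agree.

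**Effect on the summary (assumed ratios).** If one of n Day 7 values is a fraction r of typical, the geometric mean is multiplied by r^(1/n). With r = 0.5 and n = 22 this is 0.969, a fall of about 3%. With r = 0.1 and n = 18 it is 0.880, a fall of about 12%.

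**The case against.** **The Day 7 check carries its own time limit.** SAP 7.2.3 says compliance up to Day 7, which can be read as doses due up to Day 7. That reading is fair, and applying 7.7.6 there is an inference. But 7.7.6 is the only formula in the SAP, so the alternative is an undefined denominator, which also needs text.

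**The sequence is narrow.** Early terminators have no blood draw for concentrations at their final visit (Protocol Schedule of Events, footnote 7, and Section 14.2), so the child must attend Visit 3. If the supervised dose is then applied, the last-dose day becomes 7. A child who had stopped after Day 4 PM scores 9/14 = 64.3% and is rejected. This stands: the problem needs withdrawal between the draw and that dose.

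**Other safeguards exist.** A 60-hour sample breaches the draw window and might be ruled a significant deviation, but the SAP does not say so. Day 14 concentrations have the final-three-doses rule, and the adrenal analysis requires a last dose within 14 hours of the test (SAP 7.2.2), so those analyses are protected. SAP 7.8.3 also reports medians, ranges and individual plots.

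**A stronger reading fails.** A reader might infer that missed doses never count for discontinuers, that their compliance is near 100% by construction, or that the 80% check does not work at all. The 75% and 50% results above contradict each of these. Nor does a high score always mean a bad sample. A child with 13 doses through Day 7 AM, then none until withdrawal on Day 13, scores 13/14 = 92.9% against 13/24 = 54.2% of doses due through Day 12. All 12 doses before the Day 7 draw were applied, so that trough is valid and only the descriptive compliance figure is flattered.

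**Conclusion.** The point holds in a limited form. For discontinuers, doses due after the last-dose day drop out of the denominator, and no Day 7 rule on preceding doses makes up for it. The 80% check still rejects intermittent non-use but misses early stopping. As written, it can admit a Day 7 sample 48 to 84 hours after the last dose with a score of 90% or 100%.

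This rests on three things: that 7.7.6 supplies the denominator for 7.2.3, that the child is sampled and withdrawn before the clinic dose, and that the mistimed sample is not excluded as a significant deviation. The 3% to 12% fall in the geometric mean is for one such child among 18 to 22 and depends on concentration ratios the documents do not give. The direction, towards lower apparent exposure, needs only that concentrations fall after dosing stops. The correction is worth making before database lock.

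**What to change.** - **SAP 7.2.3, denominator.** Define compliance up to Day 7 as applications made divided by 12-hourly applications due from the first dose to the actual Day 7 draw. That is 12 for a Day 7 morning draw, or 10 or 14 if the visit falls on Day 6 or Day 8 (2 × 5 or 2 × 7).
- **SAP 7.2.3, preceding doses.** Extend the existing Day 14 final-three-doses data exclusion to the Day 7 draw. This removes the Day 5 PM and Day 6 AM cases that the denominator alone still passes.
- **SAP 7.7.6.** For discontinuers, count doses due up to the discontinuation decision in the descriptive compliance figure. Report separately any doses withheld as the protocol instructs, so that they are not presented as non-use.

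The cost is SAP wording and one extra derivation. The subject diary (Protocol Appendix 2) already records application times and missed doses. One or two Day 7 values may be lost, and some compliance figures will be lower.

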7.8 Safety Analyses

Summaries of the safety parameters will be provided as described below for the Safety population, unless otherwise specified.

7.8.1 Adverse Events

Adverse events (AEs) will be coded using the Medical Dictionary for Regulatory Activities (MedDRA) version 19.1. Verbatim terms will be mapped into a MedDRA system organ class (SOC) and preferred term (PT). For all AE summaries, if a subject has more than one AE within a PT, the subject is counted once in that PT. If a subject has more than one AE within a SOC, the subject is similarly counted once in that SOC.

The number and percentage of unique subjects reporting any local and systemic treatment-emergent AE will be summarized by SOC and PT. The number and percent of unique subjects reporting any local and systemic TEAE will also be summarized by SOC, PT, and maximum severity (mild, moderate, severe) and closest relationship to test article (not related, unlikely, possibly, probably related).

Serious AEs and DLTs, if any, will be listed separately.

7.8.2 HPA Axis Suppression Analysis

HPA axis responses to cosyntropin will be dichotomized to normal and abnormal. An abnormal HPA axis response (HPA suppression) is defined as a 30-minute post-stimulation serum cortisol level of ≤ 18 $\mu\text{g/dL}$ at Day 14. The proportion of subjects manifesting laboratory based evidence of adrenal suppression at Day 14 will be presented along with 95% confidence intervals for the Evaluable population. The observed serum cortisol levels (pre- and post-cosyntropin stimulation) and the changes in serum cortisol levels after stimulation at Screening, Day 14, and, if any, at follow-up visits will also be summarized.

7.8.3 Trough Concentrations

Morning trough concentrations (C_{12}) of cortexolone 17 α -propionate and cortexolone in plasma at Screening, Day 1, Day 7 and Day 14 will be summarized for the PK population using geometric mean, coefficient of variation in addition to n, mean, median, standard deviation, minimum and maximum.

Individual trough concentrations of cortexolone 17 α -propionate and cortexolone in plasma across visits will be plotted. Individual average trough concentrations of cortexolone 17 α -propionate and cortexolone will also be plotted by adrenal suppression status.

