4 STUDY DESIGN

This is an open-label, multicenter study in approximately 20 subjects 9 to <12 years of age with moderate to severe facial acne vulgaris (IGA score of 3 or 4) and obvious acne on the trunk (i.e., shoulders, upper chest, and/or back). The study will include a Screening Visit, a Baseline Visit (Day 1), and two (2) scheduled follow-up visits (Day 7 and Day 14). Subjects will apply 2 grams of the test article per application every 12 hours for 2 weeks.

The study schedule of events and assessment is presented in Table 1. Further details regarding the study may be found in the study protocol.

Table 1: Schedule of Events

PROCEDURES	Visit 1 Screening (Days -45 to -14)	Visit 2 Baseline Day 1	Visit 3 Day 7 ± 1	Visit 4 EOS ¹ Day 14 ± 2
Informed Consent/Assent	X	X ²		
Demographics	X			
Inclusion/Exclusion Criteria	X	Reconfirm eligibility		
Medical/Dermatological History	X			
Dermatologic Exam	X			
Physical Exam	X			X
Vital Signs, Height, and Weight ³	X			X
UPT ⁴ (females of childbearing potential)	X	X		X
ECG	X			X
Safety Labs (Hematology, Chemistry and Urinalysis) ⁵	X			X
Urine Drug Screen	X			
Virus Screen (HIV, HCV, HBV)	X			
Investigator's Global Assessment	Confirm eligibility	X		X
Lesion Counts	Confirm eligibility	X		
LSR Assessment		X (pre- & post-application)	X	X
PK Blood Draws ⁶	X	X	X	X
Cosyntropin Stimulation Test (CST) ⁷	X	Confirm eligibility		X
Study Medication Dispensed & Collected ⁸		X	X	X
Study Treatment (q. 12 hours)		X	X ⁹	
Percent BSA to be treated		X		
Weigh Test Article/Verify Compliance		X	X	X
AEs Evaluation	X	X	X	X
Review of Concomitant Medications & Procedures	X	X	X	X

¹ Subjects who terminate early shall complete all final visit activities designated at Day 14 with the exception of the PK blood draws.

² Subjects who were consented for longer than 45 days prior to the Baseline Visit will be re-consented prior to enrolling into the treatment phase of the trial.

³ Height and weight at Visit 1 only.

⁴ Testing will be conducted on all females of childbearing potential. UPT minimal sensitivity is 25 mIU/mL.

⁵ Laboratory test results will indicate if the subject was fasting. Screening laboratory tests will be conducted with the subject fasting and EOS laboratory tests are preferred to be in a fasting state.

⁶ PK blood draws at Visit 3 and Visit 4 will occur 12 hours (± 30 minutes) after the evening application on the prior day.

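### The missed-dose sample exclusion covers Day 14 but not Day 7, so a sample drawn 48 to 72 hours after the last dose can be reported as C12; and no within-child change, with its precision, is tabulated for endogenous cortexolone

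*SAP*

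**What the plan says.** **Who is in the PK population.** SAP 7.2.3 asks for 80% compliance by number of applications and no significant protocol deviation. Children must also "have at least one post-baseline PK blood draw within ±2 days of the scheduled visit at Days 7 and 14".

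**What removes a sample.** For a child in the population who "did not apply the final three doses prior to the PK blood draw at Day 14, their Day 14 data will be excluded", the child and the other samples stay. No matching sentence exists for Day 7. Children who leave early keep their Day 7 data "as long as their dose compliance up to Day 7 is at least 80" per cent; completers face no such interim check.

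**How compliance is counted.** SAP 7.7.6 states that "expected applications are 26 considering 13-day course of planned treatment for subjects who completed the study". For early leavers the denominator is twice the study day of the last dose.

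**When the draw should happen.** SAP section 4, Table 1, note 6: "PK blood draws at Visit 3 and Visit 4 will occur 12 hours" (± 30 minutes) after the previous evening's application. This is a schedule instruction and is not repeated as an inclusion rule. For the CST, SAP 7.2.2 does set a limit in hours: the child must have "applied the final dose no more than 14 hours prior to the start of the CST test".

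**What is reported.** Concentrations "in plasma at Screening, Day 1, Day 7 and Day 14 will be summarized for the PK population using geometric mean, coefficient of variation", plus the usual descriptive statistics. Individual values are plotted across visits, and individual averages are plotted by adrenal suppression status without naming the visits averaged. No change from baseline is listed for either analyte. SAP 7.8.4 to 7.8.6 do use it for local skin reactions, vital signs and laboratory tests.

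**The concern.** Trough plasma concentration is a primary safety endpoint (Protocol 18.2.2), measured on treatment at Day 7 and Day 14. The SAP accepts that a Day 14 value after missed final doses is not a trough and drops it, but the same lapse before Day 7 leaves the value in. Such a value tends to understate the Day 7 trough, and understating exposure is the unfavourable direction in a safety study in children.

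The second matter concerns one of the two analytes. Protocol section 1 describes cortexolone as part of the body's own corticosteroid pool, so an on-treatment value is background plus any contribution from the cream. Screening and Day 1 samples allow the two to be separated within a child, but the planned tables do not do it.

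**Working it through.** **1. The plan's own denominator.** 13 days × 2 = 26 applications, as SAP 7.7.6 states.

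**2. Tolerated misses.** 0.80 × 26 = 20.8, so at least 21 applications are needed (21/26 = 80.8%; 20/26 = 76.9% fails). A completer may miss 26 − 21 = 5.

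**3. Hours since last dose.** If *k* consecutive doses are missed just before a morning draw, the gap is 12 + 12*k* hours and compliance is (26 − *k*)/26, with Visit 4 on Day 14 and all other doses applied.

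| Missed before Day 7 draw | Hours since last dose | Compliance | In PK population | Same run before Day 14 draw |
|---|---|---|---|---|
| 1 | 24 | 96.2% | yes | dropped only if any miss triggers the rule |
| 2 | 36 | 92.3% | yes | dropped only if any miss triggers the rule |
| 3 | 48 | 88.5% | yes | value dropped |
| 4 | 60 | 84.6% | yes | value dropped |
| 5 | 72 | 80.8% | yes | value dropped |
| 6 | 84 | 76.9% | no | – |

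At five misses, the child has applied 7 of the 12 doses due before the Day 7 draw (58.3%).

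**4. Visit 4 window.** The denominator stays at 26, while 2(*d* − 1) doses fall due before a Visit 4 on Day *d*. Tolerated misses are 2(*d* − 1) − 21 = 1, 3, 5, 7, 9 for Days 12 to 16. The longest tolerated gaps are therefore 24, 48, 72, 96 and 120 hours.

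**5. Size of the bias.** The documents give no trough level or elimination rate, so only bounds and illustrations are possible.
- Arithmetic mean: for one affected child whose own trough equals the group mean, with *n* = 20 and a fraction *f* of that trough remaining, the loss is (1 − *f*)/20, or 0 to 5.0%. It is smaller for cortexolone, which has a background.
- Geometric mean (illustration): assume purely exogenous drug and a half-life *t* of 6 to 48 hours. One 72-hour sample (60 hours late) multiplies the Day 7 geometric mean by 2^(−60/(20*t*)), or 0.71 to 0.96.

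**6. Precision of the cortexolone change.** The paired 95% half-width at *n* = 20 is t(0.975, 19)/√20 = 2.093/4.472 = 0.468 × SD of the within-child differences. With equal visit SDs *s* and within-child correlation *r*, that SD is *s*√(2(1 − *r*)). The half-width is 0.66*s* at *r* = 0, 0.47*s* at *r* = 0.5 and 0.21*s* at *r* = 0.9. By-visit SDs alone do not fix *r*.

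**7. Individual averages.** If two untreated visits at level *b* and two treated visits at *b* + *D* were averaged, the result is (2*b* + 2(*b* + *D*))/4 = *b* + *D*/2.

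**The case against.** **The deviation clause covers it.** Protocol 6.2 makes the 12-hour timing before the draw mandatory, so a 48 to 72 hour lapse is a deviation. SAP 7.2.3 excludes significant deviations, and populations are fixed before analysis (SAP 7.3). This stands in part: the child could be excluded. But significance is not defined, and the SAP keeps a child with the same lapse before Day 14, removing only that sample. Exclusion is discretionary.

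**The scenario is remote.** Staff set the pre-visit dose time, and diaries and tube weights are checked at Visit 3. A run of misses followed by near-perfect dosing is unlikely. This stands, although the protocol foresees pauses: children are told to stop and call the site if irritation or rash develops (Protocol 6.3).

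**The SAP only follows the protocol.** This stands. Protocol 18.3 and 18.3.3.2 tie the final three doses to the end-of-study assessment. A reader might infer that the SAP introduced the Day 14-only limit; it did not.

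**Change is not the objective.** The objective is trough concentrations, and Protocol 18.3.2.2 asks for by-visit statistics, which the SAP supplies. A reader might infer that no estimate of change is available. That goes too far: where the same children contribute at both visits, the difference in visit means is the mean within-child change, and plots and listings show individual values. Mainly the precision is missing. SAP 7.2.3 does, however, let different children contribute at Day 7 and Day 14.

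**Conclusion.** The gap is real but narrow. With Visit 4 on Day 14, a completer's Day 7 sample taken 48 to 72 hours after the last dose can enter the C12 summary, with only an undefined deviation clause to stop it. This assumes 12-hour spacing, two doses on Day 1, all misses just before a Day 7 morning draw and all later doses applied. Gaps of 96 and 120 hours need Visit 4 on Day 15 or 16. The documents do not support saying that the Day 7 summary will be biased, or by how much.

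For cortexolone, the missing item is a paired change with its interval. It would remain a change from pre-dose in an uncontrolled study.

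Three further inferences go beyond the documents:
- The C12 label on the untreated Screening and Day 1 samples is editorial. The protocol's own endpoint calls all four visits trough measurements, and summaries are by visit.
- Halving of an on-treatment rise in the suppression-status figures would occur only if all four visits were averaged. The SAP does not say that they are.
- Protocol 10.4 lists the CST before the PK draw at Visit 4, but that does not show that cosyntropin affected the sample. Collection detail sits in a laboratory manual not available here.

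**What to change.** 1. **SAP 7.2.3:** apply the missed-dose sample exclusion to Day 7 as well as Day 14, dropping the sample and not the child. State whether missing any or all of the final three doses triggers it; under the all reading, 24 and 36 hour samples stay in. Flag Day 7 and Day 14 samples drawn outside 12 hours ± 30 minutes after the last dose, and show the C12 summary with and without them.
2. **SAP 7.8.3:** for cortexolone, add the within-child change at Day 7 and Day 14 from the SAP section 5 baseline (normally the Day 1 pre-dose value), with a paired 95% CI, described as a change from pre-dose in an uncontrolled study.
3. **Figures 14.3.2.1 and 14.3.2.2:** state that individual averages use Day 7 and Day 14 only.
4. **Check only:** confirm the order of the PK draw and the CST against the laboratory manual. Relabelling Screening and Day 1 as pre-dose is optional tidying.

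**Cost:** SAP wording and a few table rows, from samples and diary times already collected. Clock times of the PK draws must be on the eCRF, which could not be confirmed. A few Day 7 values may leave the C12 summary.
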